#### 6.4.2. Solicited Systemic Reactions

#### Definition

Solicited systemic reactions consist of nausea, vomiting, diarrhea, headache, fatigue, myalgia, arthralgia, chills, loss of appetite, malaise, or fever. They are assessed by the subject in a diary and by the investigator at specific time points stated in the protocol.

Solicited systemic reactions will be graded based on the criteria given in US Food and Drug Administration (FDA) Guidance for Industry 'Toxicity Grading Scale for Healthy Adult and Adolescent Volunteers Enrolled in Preventive Vaccine Clinical Trials'. The grades are Grade 0 (Absent), Grade 1 (Mild), Grade 2 (Moderate), Grade 3 (Severe) and Grade 4 (Potentially life threatening). Fever is graded as Mild (38.0-38.4°C), Moderate (38.5-38.9°C), Severe (39.0-40.0°C and Potentially life threatening (>40.0°C).

The solicited systemic reactions will be evaluated for the following time intervals:

- Prime immunization up to day 7 (inclusive) after prime immunization
- Boost immunization up to day 7 (inclusive) after boost immunization
- Both intervals combined

The intervals will start with the date and time of the immunization.

Clarification: The interval 'prime immunization up to day 7 after prime immunization' includes study day 1 to study day 8. This applies to the other intervals accordingly. All analyses are based on systemic reactions independent of their relatedness to IMP.

#### Analysis

Solicited systemic reactions will be analyzed in the same way as solicited local reactions (see Section 6.4.1 of the SAP).

#### 6.4.3. Adverse Events

#### Definition

For detailed information on adverse events see section 10.3 of the protocol.

Adverse events (AEs) will be coded using the Updated Version MedDRA® 23.0 including specific terms for COVID-19 to get a system organ class (SOC) and preferred term (PT) for each AE.

A treatment emergent adverse event (TEAE) is defined as any AE with an onset after the first immunization (if the AE was absent before the first immunization) or worsened after the first immunization (if the AE was present before the first immunization). AEs with an onset date more than 28 days after the last immunization will be considered as treatment emergent only if assessed as related to IMP by the investigator. AEs that cannot be determined to not be treatment emergent due to missing date or time will be defined as TEAE.

Clarification: To clarify the definition in the protocol, AEs with an onset date at the date of the first immunization will only be considered as treatment emergent if the AE occurred after the first immunization.

The TEAEs will be evaluated for the following time intervals, clarifying and harmonizing the intervals defined in the protocol:

- Prime immunization up to boost immunization or day 28 (inclusive) after initial immunization (whatever comes first)
- Boost immunization up to day 28 (inclusive) after boost immunization
- All TEAEs (regardless of relationship assessment) occurring from

- Prime immunization up to day 28 after boost immunization (inclusive).
- If no boost immunization, up to 28 days (inclusive) after prime immunization
- All TEAEs assessed as related through visit 10.

The intervals starting or ending with an immunization, will start or end with the date and time of the immunization. TEAEs are assigned to the time intervals according to their start date and time. AEs with missing date will be assigned to each of the respective intervals if it cannot be ruled out, that it belongs to the time interval.

Deviating from the protocol, the time intervals including 7 days after each immunization will not be analyzed.

AEs will be evaluated for the following time interval 'After Day 28 after boost or after prime (if no boost)':

All AEs (regardless of relationship assessment) occurring

- After day 28 after boost immunization
- o If no boost immunization, after 28 days after prime immunization

AEs are assigned to the time interval according to their start date and time. AEs with missing date will be assigned to the interval if it cannot be ruled out, that it belongs to the time interval.

Adverse events of special interest (AESI)

Enhanced respiratory disease or flu-like symptomatology not resolved after 7 days or with symptom kinetics that are inconsistent with a relationship to RNA immunization will considered AESIs. AESIs are marked in the CRF.

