#### Table 1: Dose ranging: vaccine dose regimens for younger adults aged 18 to 55 years in Part A (Cohorts 1 to 7)

		Vaccine IM dosing regimen	Part A – Cohort numbers & dose (µg) (12 subjects per cohort)						
Vaccine / mRNA type Vaccine-encoded antigen	1 Starting dose		2	3 De-escalation dose	4	5 Optional de- escalation dose	6	7	
BNT162a1 /	RBD of the SARS-CoV-2	Prime: Day 1	1А	2A	ЗА	4A a	5А	6А	
uRNA	S protein	Boost: Day 22	3 µg b	0.6 µg a	0.1 µg	2 µg e	0.3 µg	1 µg	
BNT162b1 /	RBD of the SARS-CoV-2	Prime: Day 1	1В	2В	3В	4В	5В	6В	7В
modRNA	S protein	Boost: Day 22	10 µg	30 µg	1 µg	60 µg d	50 µg	3 µg	20 µg
BNT162b2 /	Modified version of the full	Prime: Day 1	1С	2С	3С	4С а	5C ª	6С а	7С а
modRNA	length SARS-CoV-2 S protein	Boost: Day 22	10 µg	30 µg	1 µg	60 µg d	20 μg	3 µg	50 µg
BNT162c2 / saRNA	Modified version of the full length SARS-CoV-2 S protein	Prime only: Day 1	1D 0.1 μg	2D 0.3 µg	3D 0.1 µg to <3 µg с	4D 1 μg	5D a 0.6 µg	6 D а 3 µg d	
BNT162c2 /	Modified version of the full	Prime: Day 1	1Е	2Е	3E	4E a	5Е	6Е	7Е
saRNA	length SARS-CoV-2 S protein	Boost: Day 22	0.1 µg	0.3 µg	1 µg	5-10 μg c, d	0.6 µg	3 µg	5-10 µg с, d

a) All dose escalation doses used must be judged acceptable by the Safety Review Committee (SRC) before use.

b) Status 08 JUN 2020: This cohort was set on hold by the SRC after 6 subjects had been received their Day 1 dose, furthermore the SRC decided not to perform Day 22 dosing for these 6 subjects. Due to this hold, the starting dose is also the maximum dose.

c) Specific doses to be defined, but in the range given. Already given doses will not be repeated.

d) The planned maximum doses per vaccine candidate.

e) Dosing with this vaccine variant has been put on hold. Dosing may be resumed if disease prevention data for the other vaccine candidates suggest the need for additional vaccine candidates.

IM = intramuscular; RBD = Receptor Binding Domain; S protein = SARS-CoV-2 spike protein; tbd = to be defined.

Note: Currently, dosing with BNT162a1 has been deferred. Dosing may be resumed if disease prevention data for the other vaccine candidates suggest the need for additional vaccine candidates.

BioNTech SE	Clinical Trial Protocol	Page 12 of 113
	including Amendments Nos. 01 to 09	Version: 13.0
Confidential	BNT162-01	Date: 12 JAN 2022

 Table 2:

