 Dose ranging: vaccine dose regimens for older adults aged 56 to 85 years in Part A (Cohorts 8 to 10)

		Vaccine IM dosing	Part A – Cohort numbers & dose (μg) (12 subjects per cohort) a			
Vaccine / mRNA type	Vaccine-encoded antigen	regimen	8 Older adults	9 Older adults	10 Older adults	
BNT162b1 / modRNA	RBD of the SARS-CoV-2 S protein	Prime: Day 1 Boost: Day 22	8В 10 µg	9В а 20 µg	10В а 30 µg	
BNT162b2 / modRNA	Modified version of the full length SARS-CoV-2 S protein	Prime: Day 1 Boost: Day 22	8С 10 µg	9С а 20 µg	10С а 30 µg	

a) All dose escalation doses used must be judged acceptable by the Safety Review Committee (SRC) before use.

IM = intramuscular; RBD = Receptor Binding Domain; S protein = SARS-CoV-2 spike protein.

Note: The doses planned in this trial for older adults (i.e., adults aged between 56 and 85 years) reflect clinical data from the ongoing BNT162-01 and BNT162-02 trials with the vaccine candidates BNT162b1 and BNT162b2 in younger adults (aged between 18 and 55 years) and elderly (adults aged between 65 and 85 years). For details, see the BNT162 IB.

BNT162b1:

• BNT162b1 P/B doses of 1, 10, 30, and 50 µg showed acceptable tolerability in younger adults.

• Based on the tolerability profile after the prime dose at 60 µg (BNT162-01 trial) and 100 µg (BNT162-02 trial), the respective boost doses were not administered.

• BNT162b1 P/B doses of 10, 20, and 30 µg showed acceptable tolerability in elderly adults. This tolerability appears to be better than seen in younger adults at the same doses. BNT162b2:

• BNT162b2 P/B doses of 1, 10, and 30 µg showed acceptable tolerability in younger adults.

• BNT162b2 P/B doses of 10, 20, and 30 µg showed acceptable tolerability in elderly adults. This tolerability appears to be better than seen in younger adults at the same doses.

Based on the tolerability data summarized above, and the implemented safety measures (sentinel/staggered subject dosing, post-dose observations period, wellbeing questioning, etc.) as described in the section Risk assessment, the planned doses in older subjects in this trial are expected to show acceptable tolerability. Based on the available immunogenicity data after dosing with BNT162b1 and BNT162b2 in younger adults in the BNT162-02 trial (see the BNT162 IB), the doses planned in this

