# **3 OBJECTIVES AND ENDPOINTS**

Objectives	Endpoints a
Primary objective	
(All cohorts) To describe the safety and tolerability profiles of prophylactic BNT162 vaccines in healthy adults after single dose (SD; prime only) or prime/boost (P/B) immunization.	
 
Solicited local reactions at the injection site (pain, tenderness, erythema/redness, induration/swelling) recorded up to 7 d after each immunization (trial days 8 and 29).
 
Solicited systemic reactions (nausea, vomiting, diarrhea, headache, fatigue, myalgia, arthralgia, chills, loss of appetite, malaise, and fever) recorded up to 7 d after each immunization (trial days 8 and 29).
 
The proportion of subjects with at least 1 unsolicited treatment-emergent adverse event (TEAE):         
 
For BNT162a1, BNT162b1, BNT162b2, and BNT162c2 (P/B): occurring up to 21 d after the prime immunization (trial day 22) and 28 d after the boost immunization (trial day 50).
 
For BNT162c2 (SD): The proportion of subjects with at least 1 unsolicited TEAE occurring up to 28 d after the immunization (trial day 29).
 
 
 

Secondary objectives	

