#### 9.4.2 Primary endpoints

The primary endpoints are defined in Section 3.

All AEs will be coded using the most recent version of Medical Dictionary for Regulatory Activities (MedDRA®) coding system to get a system organ class (SOC) and preferred term (PT) for each AE.

Treatment-emergent AEs (TEAEs) are defined in Section 10.3.1.1 and will be summarized using the Safety Set. In general, AEs will be analyzed by group (i.e., by type [BNT162a1, BNT162b1, BNT162b2, BNT162c2 SD, and BNT162c2 P/B] and dose level) and for each immunization, i.e., for:

- Prime immunization up to 7 d after initial immunization
- Prime immunization up to boost immunization or 28 d after initial immunization (whatever comes first)
- Boost immunization up to 7 d after boost immunization (only for P/B regimens)
- Boost immunization up to 28 d after boost immunization (only for P/B regimens)
- Prime immunization up to 28 d after boost immunization or after prime immunization (if no boost was given)

Additionally, AEs will be summarized for all dose levels combined for each type.

For each analysis, the number and percentage of subjects reporting at least one AE will be summarized by PT nested within SOC for each of the following AE types using the Safety Set:

- Any AE
- Any AE excluding AEs based on solicited reporting via subject diaries
- Related AE

Clinical Trial Protocol including Amendments Nos. 01 to 09 BNT162-01 Page 83 of 113 Version: 13.0 Date: 12 JAN 2022

- Grade ≥3 AE
- Related Grade ≥3 AE
- Any SAE
- Related SAE

Moreover, the number and percentage of subjects with any AE will be summarized by worst grade by PT nested within SOC.

Local reactions and systemic reactions will be graded using criteria based on the guidance given in US FDA Guidance for Industry "Toxicity Grading Scale for Healthy Adult and Adolescent Volunteers Enrolled in Preventive Vaccine Clinical Trials" (see Section 10.3.1.11).

For each immunization, the number and percentage of subjects reporting at least one local reaction or systemic reaction (i.e., solicited data collected using subject diaries) will be summarized for each of the following types using the Safety Set:

- Any local reactions or systemic reactions
- Grade ≥3 local reactions or systemic reactions

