## 1.1. Objectives and Endpoints

Objectives	Endpoints a
Primary	
To describe the safety and tolerability profiles of prophylactic BNT162 vaccines in healthy adults after single dose (SD; prime only) or prime/boost (P/B) immunization.	
 
Solicited local reactions at the injection site (pain, tenderness, erythema/redness, induration/swelling) recorded up to 7 days (d) after each immunization (trial days 8 and 29).
 
Solicited systemic reactions (nausea, vomiting, diarrhea, headache, fatigue, myalgia, arthralgia, chills, loss of appetite, malaise, and fever) recorded up to 7 d after each immunization (trial days 8 and 29).
 
Deviating from protocol version 13.0, the endpoint related to unsolicited treatment emergent adverse events (TEAE) will be:
 
The proportion of subjects with at least 1 unsolicited treatment emergent adverse event (TEAE):         
 
o For BNT162a1, BNT162b1, BNT162b2 and BNT162c2 (P/B):
 
Occurring after prime immunization up to boost immunization or 28 d after the prime immunization (whichever comes first) and 28 d after the boost immunization.
 
o For BNT162c2 (SD):
 
 
 

Table 2: Objectives and endpoints

	The proportion of subjects with at least 1 unsolicited TEAE
	occurring up to 28 d after the immunization.
Secondary	

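### The post-prime unsolicited-TEAE proportion is counted over about 21 days in boosted subjects and 28 days in unboosted ones, and protocol Sections 3 and 9.4.2 disagree on the window

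*SAP*

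**What the plan says.** The primary endpoint in protocol Section 3 (and the synopsis) is the proportion of subjects with at least one unsolicited TEAE. For the prime/boost regimens it counts events "occurring up to 21 d after the prime immunization (trial day 22) and 28 d after the boost immunization (trial day 50". Protocol Section 9.4.2, which refers back to Section 3 for the endpoint definitions, lists a different post-prime interval for the AE analysis: "Prime immunization up to boost immunization or 28 d after initial immunization (whatever comes first".

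The SAP takes the second. Section 1.1 announces it ("Deviating from protocol version 13.0, the endpoint related to unsolicited treatment emergent adverse events (TEAE) will be") and gives the new wording: "Occurring after prime immunization up to boost immunization or 28 d after the prime immunization (whichever comes first". SAP Appendix 1 records the change, with consistency as the only reason. Section 6.4.3 puts it into effect: "Prime immunization up to boost immunization or day 28 (inclusive) after initial immunization (whatever comes first". The overall interval in Section 6.4.3 runs to 28 days after the boost, with this rule for the others: "If no boost immunization, up to 28 days (inclusive) after prime immunization".

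Two groups are documented as unboosted. For BNT162b1 60 µg, the note under protocol Table 2 cites tolerability after the prime dose and says "the respective boost doses were not administered". For BNT162a1 3 µg, footnote b of protocol Table 1 says "furthermore the SRC decided not to perform Day 22 dosing for these 6 subjects". SAP Section 6.1.1 places all cohorts of one vaccine, plus a cohort-total, as columns of the same table.

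**The concern.** The endpoint is a simple proportion, so it rises with the length of the window. Under the SAP interval that length is set by whether the boost was given, and the boost was withheld in BNT162b1 60 µg because of what happened after the first dose. Individual subjects with a dose-limiting toxicity may also go unboosted (protocol Sections 6.6.1 and 7.1). The window is thus tied to the tolerability that the endpoint is meant to describe.

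A reader who scans the BNT162b1 columns for a dose trend sees 60 µg counted over 28 days beside cohorts counted over about 21. The cohort-total mixes the two. In the overall table the same cohort is counted for less time than its neighbours. The SAP specifies no common cut-off or person-time measure for this proportion. Repeating AE analyses on the Safety Boost Set would not help, because that set leaves out the unboosted subjects.

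**Working it through.** **Inputs**
- Boost visit in the dose-ranging cohorts: Day 22 ± 2 days (protocol Table 6, footnote h), so 19 to 23 days after the prime dose, nominally 21.
- Cohorts 11 to 14: a boost delayed by illness may be given within 1 week of the scheduled day (protocol Section 7.1.1), so up to about 21 + 7 = 28 days after prime.
- No boost: 28 days (SAP Section 6.4.3).
- Planned cohort size: 12 (protocol Table 1).
- Event rate over time: not given in either document; assumed below.

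**1. The plan's own figure.** Protocol Section 9.2 gives the chance of seeing a particular TEAE of 15% incidence at least once in 12 subjects as 85.8%. Check: 1 − 0.85^12 = 0.858. It reproduces. It is not tied to a window length.

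**2. Window ratios, unboosted to boosted**
- Post-prime: 28/21 = 1.33 nominal; 28/23 = 1.22 to 28/19 = 1.47 across the permitted boost days.
- Overall: 28/(21 + 28) = 28/49 = 0.57. Appendix 1 of the SAP also includes related TEAEs through Visit 10 in this interval whether or not the boost was given, so the inequality bears on events not judged related.

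**3. Effect on the proportion if the hazard is constant.** With p21 the 21-day proportion, p(d) = 1 − (1 − p21)^(d/21).

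| p21 | 28 days | Excess | Expected subjects of 12, 21 d to 28 d |
|---|---|---|---|
| 15% | 1 − 0.85^(4/3) = 19.5% | 4.5 points | 1.80 to 2.34 |
| 30% | 1 − 0.70^(4/3) = 37.8% | 7.8 points | 3.60 to 4.54 |

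The 15% row borrows the level used in Section 9.2; the 30% row is illustrative. With the boost at 23 or 19 days, the excess is 3.2 or 5.8 points for the 15% row and 5.5 or 10.3 points for the 30% row.

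**4. If events come early.** Let the hazard between days 21 and 28 be a fraction f of the earlier hazard: p28 = 1 − (1 − p21)^(1 + f/3). For p21 = 15%, f = 1 gives 19.5%, f = 0.5 gives 17.3% and f = 0 gives 15.0%.

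**5. Overall interval, constant hazard.** For p21 = 30%, 49 days gives 1 − 0.70^(49/21) = 56.5%, against 37.8% over 28 days. This also assumes that the boost adds no risk of its own.

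**6. Scale against chance.** At 30% in 12 subjects the standard error is √(0.30 × 0.70/12) = 0.132, or 13 points. The artefact is smaller than the random error of one cohort, but it is systematic and its direction is known.

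**7. With a cut at boost or day 21, whichever is earlier.** Unboosted subjects have 21 days and boosted dose-ranging subjects 19 to 21. The ratio falls to between 1.00 and 21/19 = 1.11.

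**The case against.** The strongest reply is that the interval was not devised in the SAP. It stands in protocol Section 9.4.2 under the heading for primary endpoints, and the SAP declares its choice. The overall interval likewise follows Section 9.4.2. This stands: the root fault is a disagreement inside the protocol. A reader might infer an undisclosed change of endpoint, and the documents show the opposite.

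Twenty-eight days also has a basis. The TEAE definition (protocol Section 10.3.1) runs to 28 days after the last dose, and the single-dose endpoint uses 28 days. An unboosted subject has in effect had a single dose, and dropping days 22 to 28 from a safety table would be the less cautious choice. This also stands, and is why the SAP interval should stay. It does not make the columns comparable.

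The 21 days may also be read as approximate, since the SAP's footnote to the endpoint table says so and day 22 is simply the boost visit. That explains 19 to 23 days in boosted subjects but not 28 in the others.

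The analysis is descriptive, with no hypothesis (protocol Section 9.1), and onset can be traced in the AE listings. That limits the harm, although describing safety is the primary objective.

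Finally, constant hazard may be too pessimistic: protocol Section 2.3.1 reports that many TEAEs resemble reactogenicity, typically starting within 24 hours. Against that, the unsolicited analysis removes diary-type events that begin and end within the first 7 days, so what remains is less concentrated early. The documents do not settle the size.

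**Conclusion.** The point holds as a matter of comparability and reconciliation. Protocol Sections 3 and 9.4.2 give different post-prime windows, and the one the SAP adopts makes counting time depend on the boost: nominally 28 against 21 days, a ratio of 1.33. The overall interval is unequal in the other direction, 28 against about 49 days.

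The excess in the post-prime table would be about 4.5 points at a 21-day proportion of 15% and 7.8 points at 30%, if the hazard is constant and the boost falls on day 22. It falls towards zero if few events start after day 21.

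Three stronger readings should be avoided:
- That unboosted subjects are observed longer. They complete all scheduled assessments (notes to protocol Table 6); only the counting window differs.
- That all unboosted cohorts are compared unfairly. The one clear contrast is BNT162b1 60 µg; the Table 2 note describes prime/boost tolerability at 1, 10, 30 and 50 µg in younger adults. For BNT162a1 3 µg, with 6 subjects, further dosing is deferred and boosted comparators are not shown to exist.
- That the 28-day interval is wrong and should be removed. It is supported elsewhere in the protocol and captures events that ought to be reported.

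This is an inexpensive improvement to a descriptive safety table, not a fault that invalidates the analysis.

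**What to change.** 1. Reconcile protocol Section 3 (and the synopsis) with Section 9.4.2. If no further amendment is planned, state in SAP Appendix 1 that the two differ and which figure serves which purpose.
2. In SAP Sections 1.1 and 6.4.3, report the post-prime unsolicited-TEAE proportion to the boost or day 21, whichever is earlier, for every prime/boost subject, boosted or not. Name this as the figure for reading across cohorts.
3. Keep the SAP's boost-or-day-28 interval in full beside it, so that no event is lost.
4. Show the overall interval and the cohort-total by boost status, or per person-time.
5. Footnote the tables to name the unboosted cohorts.

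The cost is one derived flag, one extra table and some SAP wording; no data collection or clinical procedure changes. The downside is that events after day 21 appear only in the 28-day and overall tables. This affects unboosted subjects, and also boosted subjects whose boost came late: up to 23 days after prime in the dose-ranging cohorts, and up to about 28 days in Cohorts 11 to 14.
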